4.33 Longitudinal Follow Up

At the Longitudinal Follow Up Visit 1, the following data will be collected (data collected at follow up noted). This visit may occur any time after consent and after the entry US has been graded. It should occur within 4 months of determination that the subject is eligible for longitudinal follow up; Group A HTG US, Group B NL US (matched Control), Group C cirrhosis or Group D homogenous).

- 1. Medical History
 - a. Birth history: term, preterm (<36 weeks)
 - b. Diagnosis of CF:
 - i. Newborn screen (yes, no)
 - ii. Prenatal diagnosis (yes, no)
 - iii. Family History (yes, no)
 - iv. Clinical diagnosis (yes, no)
 - 1. Pulmonary presentation (acute persistent respiratory symptoms)
 - 2. GI presentation (liver problems, steatorhea/diarrhea, rectal prolapse pancreatitis)
 - 3. Meconium ileus/intestinal obstruction
 - 4. Nutritional presentation (edema, electrolyte imbalance, FTT, hypoalbuminemia)
 - c. Nutrition history: Will use the established Cystic Fibrosis Foundation Registry or the Toronto database to get their weight (wt) and height (ht) at annual visits to classify by z score
 - i. Growth parameters at 1 and 2 years of age (wt, ht and wt for ht z scores).
 - ii. Presence of diabetes
 - d. Family History
 - i. Maternal (biological mother) family history with an emphasis on liver diseases: whether child's biological mother is living, detailed liver disease history of all first order biological relatives including

the subject's mother, mother's siblings, and subject's maternal grandparents, as well as siblings of the subject.

- ii. Paternal (biological father) family history with an emphasis on liver diseases: whether child's biological father is living, detailed liver disease history of all first order biological relatives including the subject's father, father's siblings, and subject's paternal grandparents, as well as siblings of the subject.
- e. Surrogate markers for socioeconomic status: zip code of current residence, marriage status of parents, type of medical insurance of parents and subject, annual income of household and education level of parents
- 2. Current history: (Updated at follow up)
 - a. Pulmonary symptoms at baseline for the last week (yes, no)
 - b. Gastrointestinal symptoms at baseline using the Gastrointestinal Symptom Scale for Kids (GISSK)(32)
 - c. Current medications
 - i. Pancreatic enzyme supplementation (yes, no): largest dose of lipase (IU total) for a meal
 - ii. Ursodeoxycholic acid (yes, no) total daily dose (mg)
 - iii. Chronic azithromycin (yes, no)
- 3. Physical examination: (Updated at follow up)
 - a. Measurements: weight, length, BMI, triceps and subscapular skinfold thickness, mid-arm circumference
 - b. Appearance: jaundice, cyanosis, spider hemangiomas, clubbing, palmar erythema, edema, (yes, no);
 - c. Assessment of liver: liver span, texture, ascites, spleen palpable/not palpable
- 4. Laboratory data, based on standard laboratory studies obtained at least yearly by all participating centers (the study will not plan to pay for missing data): (Updated at follow up). This data will typically be collected at the subject's annual CF visit. Labs for the longitudinal follow up visit will be those collected at or after the longitudinal visit.
 - a. total bilirubin, albumin, total protein, alkaline phosphatase, AST, ALT, GGT
 - b. HCT, Hbg, WBC, platelet count, ANC (ANC = automated value on the CBC, if not available ANC = WBC times percent neutrophils+bands)
 - c. glucose,
 - d. calcium,
 - e. 25-hydroxy vitamin D, alpha tocopherol, retinol,
- 5. FVC, FEV1 (values at the most recent routine visit: Percent of predicted using the Wang and Hankinson percent predicted equations). This should not be from a period of pulmonary exacerbation. (Updated at follow up)
- 6. Presence of *Pseudomonas aeruginosa* and/or *Burkholderia cepacia* complex in the sputum (EPIC definition) (yes, no) (Updated at follow up)
- 7. Collection of urine, serum and plasma (Updated at follow up) (Biospecimen collection may be timed to coincide with the subject's annual CF labs.
- 8. Collection of blood for DNA or cell lines (Once)

- 9. Collection of DNA from parents. (Once)
- 10. Standardized abdominal US (Updated every other year)
- 11. Elastography data determined locally
- 12. Quality of Life (Yearly starting with Longitudinal Follow Up Year 1 visit)
 - a. CFQ-R Preschool Version (3-6 years old)
 - b. CFQ-R Child Version (6-13 years old)
 - c. CFQ-R parent Version (6-13 years old)
 - d. CFQ-R Teen Adult (14 and up)
 - e. CFQ-R Preschool version (3-5 years old)
 - f. PEDS QL Child Report (8-12 years old)
 - g. PEDS QL Parent Report (3-12 years old)

CFQ: This is a disease-specific, validated instrument designed to measure impact on overall health, daily life, perceived well-being and symptoms. It was developed specifically for use in patients with a diagnosis of cystic fibrosis. Three versions of the instrument have been developed: one for adults and adolescents 14 years of age and older (CFQ Teen/Adult); two for assessing children ages 6-13 years, one to be completed by the child and one to be completed by parent (CFQ Child and CFQ-Parent respectively). There is also a new tool for younger children (3-6) PEDS QL is a validated pediatric specific, validated instrument with a parent and child component valid for assessing children >7 years of age. We will use the parent report for children 3-12 years of age and the child report for children >7 years of age. This instrument has been used in PEDS C, BARC, CLiC, and ChiLDREN/ChiLDReN.

Justification: These data fields represent intake data at enrollment. The data will be important for defining baseline characteristics of study participants; evaluating familial, genetic, epidemiologic and demographic factors that may be associated with possible development of cirrhosis; assessing diagnostic accuracy and utility of clinical, laboratory, histology and imaging studies; assessing baseline liver function, pulmonary function, nutritional status, physical findings and imaging findings that may be used in the analysis of factors that predict outcomes.

Cost of study to subjects: Subjects and their third party payers will not be charged for research-related tests. These include abdominal US, questionnaires, anthropometrics, urine collection and transport, DNA collection and transport, and research serum and plasma collection and transport.

4.4 Specimens to be Collected

During this study, blood and urine specimens will be obtained, de-identified and shipped to and stored at the NIDDK repositories for use in future CFLD ancillary studies. This "biobanking" is a critical aspect of this longitudinal study to facilitate the creation of a resource of DNA and other specimens from a meaningful number of patients with CFLD. In addition, obtaining and storing DNA or EBV-transformed leukocytes (from which DNA can be extracted) will allow future studies to investigate genetic causes and influences (modifier genes) in CFLD.

4.41 Research Blood and Urine Specimens

Biological mother and father:

1. 20 ml of whole blood in two 10 ml. EDTA vials to be sent to the NIDDK contract facility for DNA extraction.

Subject at initial enrollment into this study:

- 1. Draw 9 ml (in subjects <40 kg) or 26 ml (in subjects ≥40 kg) and divide as follows:
 - $2 \text{ ml} (<40 \text{ kg}) \text{ or } 3 \text{ ml} (\geq40 \text{ kg}) \text{ for serum}$
 - $2 \text{ ml} (<40 \text{ kg}) \text{ or } 3 \text{ ml} (\geq40 \text{ kg}) \text{ for plasma}$
 - **IF** Subject <40 kg: 5.2 ml of whole blood for lymphoblasts for DNA
 - **IF** Subject \geq 40 kg: 20 ml of whole blood for DNA processing and storage.
- 2. Collect 5 ml of urine

Subject at follow up visits:

- 1. 2 ml (\leq 40 kg) or 3 ml (\geq 40 kg) for serum
- 2. $2 \text{ ml} (<40 \text{ kg}) \text{ or } 3 \text{ ml} (\geq40 \text{ kg}) 1 \text{ of whole blood for plasma}$
- 3. Collect 5 ml of urine

Total Research Blood Drawn: The total volume of blood drawn for research only purposes from children enrolled in this study is outlined in Table 2. This volume should be within acceptable limits of all IRBs at Clinical Sites.

Table 2. Total amount of research blood drawn from subjects and parents					
Visit	Amount in ml	Amount in ml	Amount in ml		
	drawn from	drawn from	drawn from		
	subjects <40 kg	subjects ≥40 kg	parents for		
	for research at	for research at	research at the		
	the visit	the visit	visit		
Initial visit	9	26	20		
Annual follow up visit	4	6			

 Table 2. Total amount of research blood drawn from subjects and parents

Storage of serum and plasma will allow for further investigations of biomarkers. Plasma will be primarily reserved for proteomic development. As such preparation and storage will follow methods designed to optimize the use of plasma for proteomic analysis (33). The serum and plasma would be processed and aliquoted within 1-2 hours and stored at - 80°C. Serum is stored as it is the most commonly available sample and should be available at a minimum for validation.

4. 42 Abdominal US

Abdominal US: This may be obtained at any time in the seven months after consent has been given.

The US examination will include a survey examination of the entire abdomen and a detailed examination of the liver and spleen to assess for presence or absence of liver

disease, including fibrosis/cirrhosis. Gray-scale images will be supplemented by Doppler ultrasound in all patients. The gray-scale images will be the determinant of longitudinal follow-up. The Doppler US will be the experimental arm of the study. US scans will be obtained after a minimum of a 4-hour fast for flow evaluation.

Liver echogenicity and contours will be assessed. Liver echogenicity will be evaluated by comparing it to that of the kidney. Irregularity or nodularity of the hepatic parenchyma and liver capsular surface, portal vein diameter, collateral vessel formation, ascites, and splenomegaly will be evaluated. Doppler US will be used to assess the presence and direction of flow in the main portal vein and right, main and left hepatic veins; and flow velocity will be assessed in the portal vein and resistive and pulsatility indices will be sought in the hepatic and splenic arteries.

To aid in statistical analysis, the liver ultrasound findings will be classified as follows:

Grade	Appearance
0	Normal (NL US)
1	Heterogeneous echogenicity
2	Diffuse homogeneous increased echogenicity
3	Heterogeneous liver texture with nodular parenchyma and margins,
	including enlargement of caudate lobe (indicates cirrhosis)(34)
4	Heterogeneous liver with nodular parenchyma and margins and at
	least 2 of the following: collateral vessels, splenomegaly, thickened
	omentum, large portal vein, reversed (hepatofugal) flow in the
	portal vein, enlargement of the hepatic arteries with increase in
	blood flow resistance (indicates portal hypertension)

There will be an initial training set and validation of consistency in the readings and grading of the US's for the participating radiologists. Center radiologists will undergo web-based training for grading of the liver ultrasounds. Centers will provide de-identified liver ultrasounds for the validation set (one of each grade). All center radiologists who will be blinded to the results, will then grade the liver ultrasound images. Results will be analyzed by the study statistician to determine inter and intra-observer reliability. A sample size of 35 ultrasounds with 7 observations per ultrasound achieves 91% power to detect an intraclass correlation of 0.700 under the alternative hypothesis when the intraclass correlation under the null hypothesis is 0.500 using an F-test with a significance level of 0.05. Center radiologists must meet the accuracy criteria outlined in the MOO before the study can start at any center.

The same training set used for the radiologists will be used to train the sonographers. In addition, there will be a written guide documenting the required images for the sonographers.

There will be ongoing assessment of the quality of the US and the consistency of the US readings. The first five US studies from each institution will be reviewed by the lead radiologist (MS) to ensure uniform quality. A scoring sheet of the image quality for each

[figure not shown]
of the first five US scans will be completed and stored at the data center and also sent to the radiologist at each institution.

For each of the US images, there will be three readings of each image and assessment of the image quality (the study site radiologist reading and 2 other radiologists). The additional readings will rotate between the radiologists in the study as outlined in the MOO.

There will be ongoing assessment of discordance over time that will be tracked as a group and by individual radiologist as outlined in the MOO. We do anticipate occasional disagreement within one grade. All discordant readings will be reviewed by the lead radiologist (MS). Criteria for interventions are outlined in the MOO.

If a new radiologist is added to the study, the process for training and verification will be the same as outlined above.

Flow Diagram of Liver US Process

4.43 Specimens Repository

Central repositories have been established by the National Institute of Diabetes and Digestive and Kidney Diseases (NIDDK), a division of the National Institutes of Health, for long-term storage for data, biological specimens and for the establishment and storage of DNA cell lines and DNA extraction. Whole blood for cell lines or DNA extraction will be shipped immediately to the NIDDK genetic repository. Biological samples will be shipped via licensed overnight carrier to the NIDDK biospecimen repository. All specimens will include a research study identifier, but otherwise will be de-identified prior to shipment to either repository. A computer log will record all incoming samples at the central repository, the storage location, and the date, and the type of sample. Receipt of samples will be acknowledged to the originating center.

NOTE: Please see the Manual of Operations for detailed instructions on specimen collection and shipping.

4.44 Specimen Use

Specimen use will be under the policies developed by the CFLD-NET steering committee during the study. Procedures for use of specimens and data after the study has ended are posted on the NIDDK repository website.

5. TERMINATION OR WITHDRAWAL OF SUBJECT PARTICIPATION

Subjects in the longitudinal follow up will be followed annually for approximately six years, through the completion of the Year 6 US and study closeout procedures. The subject or the subject's parents or guardians may request that the subject be removed from the study at any time. In addition, the investigator may withdraw a subject from the study if he/she determines that it is in the subject's best interests. Subjects who receive a liver transplant will end participation in the study.

Note: Upon request of the subject or the subject's parents or guardians, samples and data that have been submitted to the NIDDK repository or to the data coordinating center may be destroyed unless the samples have already been used or the data have been included in reported analyses or unless the linkage between the research identifier and the subject has been destroyed. When the study ends at a clinical site or the subject completes the study, the linkage between the samples and the subject will be destroyed. Once this linkage has been destroyed, it will no longer be possible to withdraw samples and data from the repository and the database in response to a subject request.

6. STATISTICAL CONSIDERATIONS

6.1 Sample Size and Power

The sample size calculations have been modified for Amendment 2 (date 5/30/2011). We have modified the calculations as the prevalence of heterogeneous US pattern in our study has not been as frequent as prior reports have suggested. Previous literature suggested a 15-20% prevalence of heterogeneous US in CF. In contrast, in this study, after 325 US studies, we have found a prevalence of 9%. Thus we have changed from matching heterogeneous US subjects 1:1 to 1:2. The sample size calculations have been further modified for Amendment 4 (11/11/2014). We have modified the calculations as the variability of US grading was shown to be larger than what has been expected prior to initiation of the study. To achieve a more reliable primary outcome, we extended the study period to 6 years after screening US and introduced an interim analysis based on year 4 US results with a more stringent definition of development of cirrhosis.

Characterizing the ability of US abnormalities to identify children at risk for progression to cirrhosis is the primary goal for this study. N =60 patients with heterogeneous livers will be compared with N = 120 patients with normal livers. Based on previous literature, in patients with a heterogeneous liver on US, 67% will progress to have US features consistent with cirrhosis and 46% will progress to portal hypertension (8). In patients

with a normal US, 7-13% will develop cirrhosis 5-7.5% will develop portal hypertension. Thus, patients with a heterogeneous liver have a 5.2 fold increased incidence of cirrhosis and a 6.1 fold increased incidence of portal hypertension compared to children with a normal US.

Based on the literature and our experience to date, we expect by Year 6 follow-up, 26% of HTGs and 8% of NLs will have converted to CIR. We will conduct an interim analysis when all longitudinal NL and HTG subjects have finished Year 4 US visit. To control for type I error with multiple tests, we consider p<0.025 to be statistically significant for both interim analysis and analysis at the end of the study.

At Year 6 follow-up, group sample sizes of 60 and 120 achieve at least 80% power to detect a difference of 18% between the null hypothesis that both group proportions are 14% and the alternative hypothesis that the proportion in the heterogeneous liver (US) group is at least 26% using a two-sided chi-square test without continuity correction and with a significance level of 0.025. This corresponds to a relative risk of developing cirrhosis in the US group of 3.25 and an odds ratio of 3.9.

Preliminary analysis suggests that the US finding of CIR may be slightly more variable than we initially believed. Thus, when conducting the interim analysis, we will use a more stringent definition of development of cirrhosis: only cases graded as CIR with agreement among 3 or more radiologists (3/4 or 4/4) in the follow-up US visits will be considered as an event of converting to CIR in Group A (NL) and B (HTG). If the interim analysis shows significant difference between Group A and Group B, we will terminate the PUSH study.

With approximately 30 subjects in Group C (cirrhosis echo pattern on screening US) and 30 subjects in Group D (homogeneous echo pattern on screening US), the precision to estimate the incidence of portal hypertension or hepatic synthetic failure, and heterogeneous liver or cirrhosis, respectively, is provided in the table below.

Incidence Rate	Precision (Standard Error)		
0.05	0.040		
0.10	0.055		
0.15	0.065		
0.20	0.073		
0.25	0.079		

6.2. Analysis Plan

Outcome Variables

The specific aims of this study are to determine if imaging changes identified by ultrasound (US) predict the risk of progression of liver disease by comparing subjects with heterogeneous livers to those with normal livers.

The Primary Outcome is the development of cirrhosis

• Cirrhosis will be defined by imaging criteria (Grade 3 or 4 as described in 4.4 Section on US Grading) in group A or B

Secondary outcomes relate to effect on associated pulmonary and nutritional issues, signs and symptoms of portal hypertension and markers of hepatic synthetic function:

- Health related quality of life
- Growth (length, weight and BMI Z-score, anthropometrics)
- AST, ALT, GGTP
- FEV1, FVC
- Sputum Culture (Pseudomonas, Burkholderia cepacia)
- Use of IV antibiotics
- Hospitalization for treatment of pulmonary exacerbation
- CBC (WBC, Hbg, ANC, platelet count)
- Fat soluble vitamin levels (Vitamin E, 25 hydroxy vitamin D, Vitamin A)
- Appearance of signs or symptoms of portal hypertension among children with cirrhosis discovered during the study, including ultrasound findings and clinical symptoms
- Development of cirrhosis amongst children with homogeneous echogenicity at screening

Prediction of Cirrhosis from US: Chi square test of independence, logistic regression and multiple logistic regression will be used to assess the odds of developing cirrhosis between those with heterogeneous livers (Group A compared with patients with normal livers (Group B). Since data will be collected longitudinally, Cox Regression with time dependent covariates will also be used to examine time to onset of cirrhosis.

Analysis of Secondary outcomes: Mixed model longitudinal data analysis will be used to compare Group A and Group B over time on health related quality of life, growth (length, weight and BMI Z-score, anthropometrics, body composition), AST, ALT, GGTP, PT, INR, FEV1, rate of change in other PFTs, CBC (WBC, platelet count), spleen size on ultrasound and fat soluble vitamin levels. Logistic regression and general estimating equations will be used to compare results of Sputum Culture (Pseudomonas), use of IV antibiotics, and hospitalization for treatment of pulmonary exacerbation.

For subjects in Groups C (cirrhosis on screening US) and D (homogeneous echogenicity on screening US), the analytic goal is estimation of the incidence of portal hypertension analysis of hepatic synthetic function, and the incidence of progression to heterogeneous liver or cirrhosis. Exact confidence intervals will be calculated.

Descriptive statistics will be provided for each of the secondary outcomes for the subjects in each of the groups defined by screening ultrasound: heterogeneous (Group A), normal (Group B), cirrhosis (Group C) and homogeneous (Group D).

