1. OBJECTIVES

The primary objective of this prospective longitudinal study is to determine the utility of abdominal ultrasound (US) at enrollment to predict the development of cirrhosis in subjects with cystic fibrosis (CF) within approximately a six year period. This is a multi-center prospective longitudinal study of pancreatic insufficient children with CF who are enrolled at age 3 through 12 years. Subjects will be prospectively ascertained, enrolled and followed at yearly intervals for approximately six years, through the completion of the Year 6 US and study closeout procedures. This longitudinal study will involve the collection of clinical and outcome data at annual intervals for six years and standardized US at 2 year intervals, including Year 2, Year 4 and Year 6. The study will test the hypothesis that a heterogeneous echo pattern on ultrasound of the liver of children with CF will predict an increased risk for the development of cirrhosis. The development of the serum and urine repository, and the maintenance of a DNA bank or transformed cell lines for DNA analyses, will be an invaluable tool for current and future ancillary investigations into the pathogenesis of the development of cirrhosis in CF and the development of biomarkers and genetic markers that would be useful in identifying patients at risk of progression to cirrhosis. Data from this study will be stored and analyzed in a secure research database at the Data Coordinating Center (DCC), University of Michigan.

The study population will consist of individuals with cystic fibrosis, who are pancreatic insufficient, 3 through 12 years of age at time of enrollment and without known cirrhosis at the time of screening. In order to study the predictive ability of abdominal ultrasound, subjects will be followed for approximately six years, through the completion of the Year 6 US and study closeout procedures.

This study will:

- 1. collect detailed clinical and demographic information about each subject at enrollment and during follow up,
- 2. obtain and store imaging data from the subject at entry and during follow up,
- 3. obtain and store serum, plasma and urine samples from the subject at entry and during follow up,
- 4. obtain and store DNA from the subject,
- 5. obtain and store DNA from the biological parents,
- 6. obtain and store quality of life data from the subject and parents at enrollment and during follow up

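### The Group A v B comparison is powered and led by yes/no methods that need a Year 6 status for every child; the one method that uses partial follow-up is secondary and carries time-dependent covariates

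*Protocol*

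**What the plan says.** - **Objective (section 1).** The aim is to predict cirrhosis over about six years from ultrasound at enrolment, with "standardized US at 2 year intervals, including Year 2, Year 4 and Year 6".
- **Power (section 6.1).** The expectation at Year 6 is that "26% of HTGs and 8% of NLs will have converted to CIR". The stated result is that "group sample sizes of 60 and 120 achieve at least 80% power", "using a two-sided chi-square test without continuity correction and with a significance level of 0.025". There is no allowance for loss.
- **Analysis (section 6.2).** Chi-square, logistic and multiple logistic regression come first for cirrhosis in Group A (heterogeneous) against Group B (normal). Because the data are longitudinal, "Cox Regression with time dependent covariates will also be used to examine time to onset of cirrhosis". No method is labelled primary and no covariate is named.
- **Leaving the study (section 5).** Families may withdraw a child at any time, the investigator may withdraw a child, and a liver transplant ends participation. Section 10 adds re-consent for those who turn 18.

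**The concern.** A yes/no method over six years has no natural place for a child scanned clear at Year 2 or Year 4 who then leaves. The child must be excluded or given a status, and neither choice returns the six-year risk when loss occurs. That risk is what the study sets out to measure, and what families and later prevention trials would use.

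The plan does contain a method that handles such children, but it stands behind the binary ones and is specified with time-dependent covariates. Values updated after the screening scan may lie between the baseline echo pattern and cirrhosis. Adjusting for them can take away part of what the baseline pattern predicts, so the result no longer answers the question in section 1.

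**Working it through.** **Step 1: the plan's own power.** Inputs from section 6.1: n = 60 and 120, risks 0.26 and 0.08, two-sided 0.025, so z = 2.241. The pooled proportion is (60 × 0.26 + 120 × 0.08)/180 = 25.2/180 = 0.14.

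- SE under the null: √(0.14 × 0.86 × (1/60 + 1/120)) = 0.0549
- SE under the alternative: √(0.26 × 0.74/60 + 0.08 × 0.92/120) = 0.0618
- Power = Φ((0.18 − 2.241 × 0.0549)/0.0618) = Φ(0.92) = 82.2%

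The stated figure of at least 80% reproduces, with complete follow-up. Exact enumeration gives 84.0%.

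**Step 2: chi-square with leavers dropped.** The protocol gives no dropout rate, so equal loss of 5% to 30% is assumed. The same formula with fewer children (for example 48 and 96 at 20% loss) gives:

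| Loss | 5% | 10% | 15% | 20% | 30% |
|---|---|---|---|---|---|
| Power | 80.2% | 78.0% | 75.7% | 73.1% | 67.3% |

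**Step 3: what a visit-based test recovers.** Simulation with constant hazards reaching 26%/8% at Year 6, dropout at a constant rate unrelated to onset, detection at Years 2, 4 and 6, and two-sided 0.025. At 20% loss:

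- chi-square in children with a Year 6 scan only: about 74% to 75%
- chi-square keeping conversions detected before exit: about 78%
- visit-based log-rank: about 78.5%

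The gain is about 4 points over completers only. It is 1 point or less if detected conversions are kept.

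**Step 4: the six-year risks at 20% loss.** Under the same assumptions, the chance of still being in follow-up at Years 2, 4 and 6 is 0.8^(1/3) = 0.928, 0.8^(2/3) = 0.862 and 0.8. The risk arising in each interval is:

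- Group A: 0.0955, 0.0864, 0.0781 (sum 0.26)
- Group B: 0.0274, 0.0267, 0.0259 (sum 0.08)

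Detected conversions are the sum of interval risk × retention:

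- A: 0.0955 × 0.928 + 0.0864 × 0.862 + 0.0781 × 0.8 = 0.226
- B: 0.0274 × 0.928 + 0.0267 × 0.862 + 0.0259 × 0.8 = 0.069

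| Handling of leavers not yet converted | Group A | Group B | Risk ratio |
|---|---|---|---|
| Counted as clear | 22.6% | 6.9% | 3.26 |
| Excluded: A 0.226/(0.226 + 0.74 × 0.8); B 0.069/(0.069 + 0.92 × 0.8) | 27.6% | 8.6% | 3.21 |
| Visit-based estimate | 26% | 8% | 3.25 |

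Under equal loss the risk ratio barely moves; the absolute risks do.

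**Step 5: unequal loss, leavers counted clear.** In the extreme case where none of the leavers' conversions is seen:

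- 20% loss in A and 10% in B: (0.26 × 0.8)/(0.08 × 0.9) = 2.89
- 10% loss in A and 20% in B: (0.26 × 0.9)/(0.08 × 0.8) = 3.66

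The planned value is 0.26/0.08 = 3.25. Where conversions detected before exit are kept, the distortion is smaller but in the same direction.

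**Step 6: does dating onset to the scan harm Cox?** The true hazard ratio is ln(0.74)/ln(0.92) = 3.61. Large-sample fits with Efron ties gave 3.58 from scan dates against 3.62 from exact times with no loss, and 3.67 against 3.60 with 20% loss. Power at 60/120 with 20% loss was about 76% against 77%. These differences are within simulation error.

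**The case against.** The strongest reply is that the plan already contains the answer. Cox censors a child at the last clear scan, and section 6.2 adds it precisely because follow-up is longitudinal. This stands: a reader might infer that the Cox model also drops early leavers or counts them cirrhosis-free, and it does neither. Only children lost before the Year 2 scan contribute nothing.

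A reader might also infer that Cox is invalid because onset is known only to within two years. The protocol states no event-date convention, and step 6 shows that dating onset to the scan leaves the group comparison essentially unchanged, since both groups share one scan schedule. That is not an error.

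Three further objections have force:

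- **Rule for leavers.** The protocol does not say that leavers are excluded or coded clear. Such a rule is commonly left to a statistical analysis plan, which is not at hand, so its absence is not held against the protocol.
- **Power.** Most of the power loss is lost information that no test recovers. A claim of a large gain from changing the test would hold only if conversions already detected were thrown away, which the outcome definition does not suggest.
- **Covariates.** None is named. Updated Doppler values or biomarkers could properly be studied this way under hypotheses 2 and 5, and the binary models still address baseline prediction.

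What survives is the ordering of methods. Both ways of forcing leavers into a yes/no analysis while keeping detected conversions move the six-year risks, in opposite directions. The method that avoids this is subordinate and is specified in a form unsuited to the main question.

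**Conclusion.** The point holds as a worthwhile improvement, not as a flaw that invalidates the comparison. The methods that carry the power statement and head the analysis section do not fit a six-year follow-up in which exits are foreseen.

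At an assumed 20% equal loss, the main consequence is a shift in the six-year risks from 26%/8% to about 27.6%/8.6% or 22.6%/6.9%, depending on how leavers are handled. The power cost is about 4 points if only completers are used and about 1 point if detected conversions are kept. The risk ratio is nearly unaffected unless loss differs between groups.

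These sizes rest on assumed dropout rates, constant hazards, and loss unrelated to liver disease. Transplant exits would not meet the last assumption under any of the methods. That chi-square is the main test is inferred from the power statement, because section 6.2 labels none. Whether the time-dependent covariates would in fact dilute the baseline effect cannot be judged, since none is named; the mismatch is with the stated objective.

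**What to change.** In section 6.2:

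1. Name as the main Group A v B analysis a discrete-time model (for example complementary log-log) over the 0–2, 2–4 and 4–6 year scan intervals. Each child contributes every interval that ends in a completed scan, up to the first scan showing cirrhosis.
2. Include the screening ultrasound group and baseline covariates only, adjusted for the matching factors in section 4.24 (age, center and *Pseudomonas* status). With about 25 expected events, keep the adjustment sparing, particularly for center.
3. Derive the six-year risks in each group from this model.
4. Keep chi-square and logistic regression as supportive analyses.
5. Confine any Cox model with time-dependent covariates to secondary questions, such as updated Doppler or biomarker values.

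The cost is wording in section 6.2 and a slightly more complex model to explain. No extra data or visits are needed. The change does not replace information lost to dropout, so it does not restore the planned power by itself.
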